3.1.3 Secondary Objectives: Safety

The secondary safety objectives are:

- To compare the safety and tolerability of BEGEDINA and conventional therapy.
- To gather additional information on the safety of BEGEDINA in subjects with Grades II-IV acute GvHD, who have failed to respond to steroid treatment.
- To evaluate the immunogenicity of BEGEDINA.
- To evaluate the effect of BEGEDINA on glucose metabolism.
- To compare the incidence of second malignancies at the end of the follow-up between BEGEDINA and conventional therapy.

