4.0 INVESTIGATIONAL PLAN

4.1 Summary of Study Design

This will be a prospective, multicenter, randomized, open-label, phase II/III clinical study in which subjects will be randomly assigned in a 1:1 ratio to receive BEGEDINA treatment or the best conventional treatment. Randomization will be stratified by the baseline GvHD severity grade to either Grade B GvHD or Grade C/D GvHD.

The study will be conducted at approximately 30 bone marrow transplantation units in Europe, US and Canada. It is planned to enroll 184 subjects with steroid-resistant acute GvHD. The subjects will be randomized (1:1) to one of two treatment arms:

- BEGEDINA IV at a dose of 2.7 mg/m²/day for 5 consecutive days from Study Day 1 through to Study Day 5, and on Study Days 10, 14, 17, 21, 24, and 28.*
- Conventional second-line treatment: a single treatment (agent), chosen at the discretion of the investigator (physician's best choice) and based on the clinical conditions of the individual subject. The treatment will be given as per prescribing instructions (and/or standard practice of the center).

Patients in both arms are to continue (or initiate) baseline therapy of methylprednisolone (or other steroid equivalent) and calcineurin inhibitor (see Section 5.7.2.4.1).

*Please note: the term "Study Day" as used throughout the protocol is used in relation to the day that randomized study treatment started and not in relation to the day of transplant.

All subjects will undergo a screening visit to assess for eligibility and for screening assessments; this visit must take place within 2 days of Baseline. After screening, subjects will undergo randomization and the baseline visit, which is also the first day of study treatment (Study Day 1) (i.e., subjects must commence study treatment within two days of meeting eligibility). Study visits will be conducted at various timepoints (Table 19) through Study Day 180.

The experimental phase of the study will end for each subject on Study Day 180. An extended, long-term, observational follow-up is also planned in order to capture survival, response/relapse, glucose metabolism, health outcomes and safety data out to Study Day 180. Thus, the expected duration for an individual subject who completes the study according to the protocol will be approximately 6 months, including screening and 180-day follow-up.

Table 19 Schedule of Events

Study Day Visit Windows Assessments	Screening ^a	Experimental Phase																		Early Withdrawal	

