6.2 Safety

6.2.1 Adverse Events

The investigator is responsible for recording all AEs observed in during the study, from the time that informed consent is signed through Study Day 58 or up to 30 days after the last dose of study treatment, whichever is later; at that time, any ongoing adverse drug reaction (ADR) and/or SAE event are to be followed until resolution (up to Study Day 180). AEs will be recorded in the subject's eCRF.

Second malignancies and deaths will be recorded as SAEs through Study Day 180.

Information about all AEs, whether volunteered by the subject, discovered by investigator questioning, or detected through physical examination, laboratory test or other means, will be collected and recorded on the AE page of the eCRF and followed as appropriate.

Diagnostic and therapeutic non-invasive and invasive (i.e. surgical) procedures will not be reported as AEs. However, the medical condition for which the procedure was performed must be reported if it meets the definition of an AE, unless it is a pre-existing (prior to stem cell transplantation (SCT)/chemotherapy) condition.

Underlying disease being studied (GvHD) will not be reported as an AE, unless is deemed as more severe than expected.

Medical conditions/diseases present before starting study drug are only considered AEs if they worsen after starting study treatment.

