8.1 Determination of Sample Size

This study will have two primary efficacy endpoints (see Section 6.1.1).

For the primary efficacy endpoint OR at Study Day 28, it is assumed that the conventional treatment would have a response rate of 50%, and further assumed that the response rate for the BEGEDINA treatment arm would be 75%. In order to have 80% power for a one-sided test at $\alpha=0.025$, 58 patients per treatment group would be required.

For the other primary endpoint, TRM up to Study Day 180, the cumulative incidence for the conventional treatment is assumed to be 50% and the one for BEGEDINA is assumed to be 30% (relative reduction by 40%). 80% power for a one-sided log-rank test with significance level 0.025 requires a total of 103 deaths without prior diagnosis of relapse. These can be expected with 92 subjects per treatment group, provided there are no early dropouts and no diagnoses of relapse. If drop-outs or diagnoses of relapse are observed during the recruitment period, the sample size may be slightly increased, e.g., to 100 subjects per treatment group. Since the required sample size for TRM is larger than the one for overall response, a total sample size of 184 (up to 200, respectively) will be used.

Overall survival up to 180 days is the key secondary endpoint and the planned sample size provides adequate power to reject the null hypothesis of equal OS, assuming 20 to 25 percent differences in survival probabilities in favor of BEGEDINA.

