8.3.7 Safety Analyses

For each study treatment, numbers of AEs and incidence rates will be tabulated by MedDRA system organ class and preferred term. An event that occurred one or more times on the date of, or subsequent to, randomization will contribute one observation to the numerator of the incidence rate. The denominator of the rate will comprise all randomized subjects exposed to the study treatment. If the intensity or seriousness of the AE changes, then the overall intensity or seriousness will be the maximum intensity or seriousness of the multiple occurrences.

Serious adverse events, AEs leading to death and AEs leading to withdrawal of subjects will be tabulated for each treatment group. Commonly occurring AEs, i.e. those which occur in 5% or more of the subjects in either treatment group, will be summarized using descriptive statistics.

Descriptive statistics will be used to present physical examination results, weight, BMI, vital signs measurements; clinical laboratory test results; and ECG results – for both raw values and change from baseline. Shift tables will be presented for selected tests.

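### An overall SAE incidence would pool deaths to Day 180 with non-fatal SAEs from a shorter window, so a survival benefit could mask an excess of non-fatal serious harm

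*Combined protocol and SAP*

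**What the plan says.** Section 3.1.3 makes the comparison a stated objective: "To compare the safety and tolerability of BEGEDINA and conventional therapy".

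Section 6.2.1 (and footnote w of the Schedule of Events, Table 19) sets two collection windows. Adverse events in general are recorded from consent "through Study Day 58 or up to 30 days after the last dose of study treatment, whichever is later". For two kinds of event the window is longer: "Second malignancies and deaths will be recorded as SAEs through Study Day 180". No cause of death is excepted.

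Section 8.3.7 counts events from randomization onward and gives no last day. On serious events it says: "Serious adverse events, AEs leading to death and AEs leading to withdrawal of subjects will be tabulated for each treatment group". It plans no fatal/non-fatal split of SAEs, no common cut-off, no adjustment for exposure or for death as a competing event, and no test of SAEs.

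Section 5.9 allows a further full BEGEDINA course for a flare after Day 28 and before Day 90, and allows conventional therapy to be continued or restarted. Either moves the last dose, and so the end of SAE collection.

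**The concern.** A subject who dies on Day 150 is an SAE subject. A subject who has a serious but non-fatal infection on Day 150, long after the last dose, is not. If both kinds of event enter one percentage per arm, that percentage falls when mortality falls, whatever happens to non-fatal serious events.

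The trial is designed to show lower mortality on BEGEDINA. If it succeeds, the same deaths that support the efficacy claim would also lower the BEGEDINA SAE rate and could read as a safety advantage. The question under Section 3.1.3, whether BEGEDINA causes more serious harm than conventional therapy, would be poorly answered in just that case.

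**Working it through.** **Inputs**

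- Day-180 transplant-related mortality, Section 8.1: "the cumulative incidence for the conventional treatment is assumed to be 50% and the one for BEGEDINA is assumed to be 30" per cent. I use these as the probability of any death, *D*. The same calculation assumes no relapse, and without relapse every death is transplant-related under Section 6.1.1.2.
- Arm size, Section 8.1: "These can be expected with 92 subjects per treatment group, provided there are no early dropouts and no diagnoses of relapse". Allocation is 1:1 (Section 4.1).
- Non-fatal SAE rate *S* by arm: not given in the documents. Assumed control range 30% to 65%.

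**1. The plan's own figure.** Comparing 50% with 30% at one-sided 0.025 and 80% power needs 93 per arm. By log-rank, HR = ln 0.7 / ln 0.5 = 0.515, which needs 72 events (Schoenfeld); 72 / 0.40 = 180 subjects, or 90 per arm. The stated 92 agrees, so 50% and 30% are the rates behind the design. The stated 103 deaths does not follow from them (92 × 0.50 + 92 × 0.30 = 73.6). That is a separate matter and is not used here.

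**2. Windows.** Day 58 is a minimum. A flare course starting on Day 89 has its last dose on Day 89 + 27 = 116, so collection runs to Day 116 + 30 = 146. Conventional therapy has no fixed end. The non-fatal window can therefore differ by subject and by arm.

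**3. What an overall rate would show.** If non-fatal SAEs are independent of death, P(any SAE) = 1 − (1 − *D*)(1 − *S*).

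| True non-fatal rate, control / BEGEDINA | Control shows | BEGEDINA shows |
|---|---|---|
| 40% / 40% | 1 − 0.5 × 0.6 = 70% | 1 − 0.7 × 0.6 = 58% |
| 40% / 50% | 70% | 1 − 0.7 × 0.5 = 65% |
| 40% / 57.1% | 70% | 1 − 0.7 × 0.429 = 70% |

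**4. Excess that is fully hidden.** Setting the two rates equal gives

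excess = (1 − *S*control) × [1 − (1 − *D*control)/(1 − *D*BEGEDINA)].

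The bracket is 1 − 0.5/0.7 = 0.286 for 50% vs 30% deaths, and 1 − 0.5/0.6 = 0.167 for 50% vs 40%.

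| Assumed control *S* | 50% vs 30% deaths | 50% vs 40% deaths |
|---|---|---|
| 30% | 20.0 points | 11.7 points |
| 50% | 14.3 | 8.3 |
| 65% | 10.0 | 5.8 |

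With equal mortality the bracket is zero and nothing is fully hidden. At 40% deaths in both arms a 20-point excess shows as 0.6 × 20 = 12 points, and a 10-point excess as 6.

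**5. Dependence.** Suppose non-fatal SAEs are twice as common in subjects who die. At control *S* = 30%, survivors' rate is 0.30/1.5 = 0.20 and the overall rate is 0.5 + 0.5 × 0.20 = 60%. BEGEDINA reaches 60% with a survivors' rate of 0.429, so its *S* is 0.3 × 0.857 + 0.7 × 0.429 = 55.7%, a hidden excess of 25.7 points. At 65% the same method gives 6.7 points. With the greatest possible overlap the overall rate is max(*S*, *D*): 40% / 50% shows as 50% / 50%, but 65% / 75% shows as 65% / 75%, fully visible.

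**6. Would a common window be enough?** At a constant hazard, deaths by Day 58 are 1 − 0.5^(58/180) = 20.0% and 1 − 0.7^(58/180) = 10.9%. Cutting deaths at Day 58 as well, but still pooling, lowers the hidden excess to 7.2, 5.1 and 3.6 points at control *S* of 30%, 50% and 65%. The longer death window causes about two thirds of the masking; the pooling causes the rest.

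**The case against.** Several points on the other side stand.

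- **Section 8.3.7 does not define a single any-SAE percentage.** It says SAEs are tabulated, and adverse events are otherwise shown by system organ class and preferred term. In that layout a relapse death and a serious infection fall in different rows. This limits the point to any overall SAE incidence. It does not remove it: an infection row can still mix non-fatal events from the shorter window with fatal ones to Day 180, and Section 2.1.1.1.2 says mortality here is mainly from infections and multi-organ failure.
- **A reader might infer that non-fatal SAEs stop at about Day 58.** The documents do not support that. Day 58 is a minimum, second malignancies run to Day 180, and Section 6.2.1.3 asks for any SAE in the course of the study, which leaves the end date less clear. BEGEDINA re-treatment would tend to raise its non-fatal count.
- **A reader might infer that the SAE comparison largely repeats the mortality endpoint.** That fits control, where at the break-even point deaths are 77% to 61% of SAE subjects (0.50/0.65 to 0.50/0.825). On BEGEDINA they are 46% to 36%.
- **Deaths are visible elsewhere**, in the table of AEs leading to death and in the TRM and OS analyses, and no test or decision rest on SAEs. This is true, but the separate tables only bound the non-fatal rate. With any-SAE 65% and deaths 30%, BEGEDINA's non-fatal rate lies between 35% and 65%; with 70% and 50%, control's lies between 20% and 70%. The sign of the difference cannot be recovered.
- **A bare Day-58 table of non-fatal SAEs has its own faults.** It would drop events during flare re-treatment, and the arm with fewer deaths has more time at risk. The fix has to deal with both.

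**Conclusion.** The concern holds in limited form. The windows differ by type of event and can differ by arm. Section 8.3.7 neither aligns them nor separates fatal from non-fatal SAEs, so any overall SAE incidence built from it is heavily driven by mortality.

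The size is conditional. A hidden excess of 20 to 10 points needs the full 50% vs 30% benefit, independence of non-fatal SAEs from death, and assumed control rates of 30% to 65%. With 50% vs 40% deaths it is about 12 to 6 points. Without a survival difference an excess is diluted but not hidden. It would be too strong to say that the SAE table will favour BEGEDINA, or that 10 to 20 points will be lost. No efficacy conclusion is affected; what suffers is a stated comparative safety objective.

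**What to change.** In Section 8.3.7, and in the SAP to which Section 8.0 refers for detail, specify:

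- (a) Non-fatal SAEs with onset from randomization through Study Day 58, the minimum window common to both arms, by arm with risk difference and 95% CI. Add cumulative incidence with death as a competing event, read beside (b) so that longer survival is not mistaken for toxicity.
- (b) Fatal SAEs through Day 58, in a separate table.
- (c) Deaths to Day 180 by cause, presented as mortality and not added to the SAE incidence.
- (d) SAEs with onset after Day 58, including those during flare re-treatment, shown separately with exposure-adjusted rates whose denominator is the time each subject was under SAE collection.

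The cost is SAP wording and a few more tables from data already collected. The SAE comparison may look less favourable to BEGEDINA. Precision is limited: with 92 per arm and two-sided 0.05, a non-fatal comparison has power 0.80 for 30% vs 50% but only 0.31 for 65% vs 75%, so the interval in (a) should be read as an estimate and a non-significant difference not taken as reassurance.

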8.3.8 Missing Data

Appropriate missing data techniques will be implemented for relevant efficacy endpoints. Multiple imputation will be used as the primary method for accounting for missing data. Details will be described in the SAP.

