6.1 Efficacy

6.1.1 Primary Efficacy

There are two primary endpoints.

1. The OR (CR or PR) at Study Day 28.
2. TRM (any deaths without prior diagnosis of relapse) up to Study Day 180

These endpoints are both considered primary as health authorities (EMA/FDA) have requested different primary endpoints.

6.1.1.1 Overall Response to Treatment at Study Day 28

The change in grade from baseline to Study Day 28 (-1/+2 day) will be used to determine the response of GvHD to treatment using the following classifications:

- *Complete response (CR)*: complete resolution of all signs of GvHD.
- *Partial response (PR)*: improvement of 1 overall grade (i.e., change from baseline in IBMTR to a less severe grading).
- *Stable disease (SD)*: No change in GvHD grading (i.e., no change from baseline in IBMTR grade).
- *Disease progression (PD)*: Deterioration in one overall grade in GvHD (i.e., worsening in IBMTR by at least 1 grade compared to baseline).
- Death (up to Study Day 28).

Overall response at Study Day 28 (i.e. change in GvHD grade compared to baseline) is defined as

- Complete response or PR at Study Day 28 response assessment
- and no third-line therapy has been introduced prior to the Study Day 28 response assessment

Non-response at Study Day 28 is defined as

- Stable disease or PD or missing response assessment at Study Day 28 (including death up to Study Day 28) or
- Complete response or PR at Study Day 28 response assessment and third-line therapy has been introduced prior to the Study Day 28 response assessment

Response at Study Day 28 will be adjudicated by an independent blinded hematologist; this adjudicated response will be used for the primary analysis of OR at Study Day 28.

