6.2.4.2 Concomitant Medication and Supportive Therapy

Information on all concomitant medications will be collected for this study, including information on all concomitant therapy to treat acute GvHD. All pharmacologic and nonpharmacologic treatment used by study subjects to treat acute GvHD prior to screening should be recorded in the corresponding eCRF. This will include the treatment for HSCT procedure.

Subjects will continue to be treated with a stable dose of systemic steroid therapy until able to be tapered following response (at least 1 stage in 1 organ) to treatment (see section [5.7.2.4.1](#)). Subjects may also continue any prior therapy used for prophylaxis at a stable dose from baseline if the therapy agent was not discontinued and restarted after initiating first-line steroid treatment for acute GvHD. No other GvHD medications are to be introduced to subjects during the initial 28 days post-BEGEDINA administration unless disease has progressed. Addition of other agents prior to Study Day 28 would constitute failure to respond (endpoint OR at Study Day 28), however the subject will remain on study for follow-up.

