8.0 STATISTICS

The SAP will be finalized prior to randomization of the first 30% of the planned number of subjects. Further statistical details can be found by referring to the SAP. The basis for the analysis plan can be found in this section.

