8.2 Analysis Sets

Full Analysis Set

The FAS comprises all subjects to whom study treatment has been randomized. Statistical analyses will be based on study treatment groups as per randomization (and strata used within randomization), irrespective of the study treatment actually received. The FAS will be used for demographics, baseline disease characteristics and all efficacy analyses.

Safety Analysis Set

The Safety Analysis Set (SAF) includes all subjects who received at least one dose of study treatment. Subjects will be analyzed according to the study treatment (regimen) they actually received: if a subject has received any dose of BEGEDINA, the subject is assigned to the

Confidential

BEGEDINA group within the Safety Analysis Set; otherwise the subject is assigned to the conventional treatment group. The Safety Analysis Set will be used for all safety analyses.

Pharmacokinetic analysis set

The pharmacokinetic analysis set consists of all subjects randomized to BEGEDINA with at least one study drug concentration value.

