8.3.4 Analysis of Primary Efficacy Endpoints

There are two primary efficacy endpoints as health authorities (EMA/FDA) have requested different primary endpoints: OR at Study Day 28 (see Section 6.1.1.1) is the single primary

endpoint for FDA, TRM up to Day 180 (see [Section 6.1.1.2](#)) is the single primary endpoint for EMA. The analysis methods are:

- the null hypothesis of equal OR probabilities for BEGEDINA and conventional treatment will be tested using a Cochran-Mantel-Haenszel test stratified for baseline GvHD severity grade (as used in the randomization) at the one-sided $\alpha = 0.025$ level. The treatment effect will be expressed as odds ratio with a two-sided 95% CI.
- TRM up to Study Day 180 will be graphically displayed by non-parametric cumulative incidence curve estimates. The null hypothesis of same TRM (defined as death without prior diagnosis of relapse) cumulative incidences for both study treatments will be tested by a one-sided test stratified for the baseline GvHD severity grade (as used in the randomization) taken into account the competing risk of relapse diagnosis. The one-sided significance level is set to $\alpha = 0.025$. Regression analysis of cause-specific hazards stratified for the baseline GvHD severity will be performed as supportive analysis in order to quantify the treatment effect in terms of hazard ratios and two-sided 95% CI.

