8.3.5.2 Analysis of Other Secondary Efficacy Endpoints

All other secondary and supportive analyses will be tested at a one-sided $\alpha=0.025$ significance level (where applicable), with no adjustments for multiplicity. These endpoints and their statistical analysis method are:

- Change from baseline in stages of GvHD by target organ at Study Day 28: shift tables displaying the frequencies for each possible change from baseline to Study Day 28.
- Cumulative incidence of chronic GvHD up to Study Day 180 will be graphically displayed by non-parametric cumulative incidence curve estimates. The null hypothesis of same cumulative incidences (up to Study Day 180) for both study treatments will be tested by a one-sided test stratified for the baseline GvHD severity grade, taken into account the competing risk of death. Stratified regression analysis of cause-specific hazards will be performed as supportive analysis in order to quantify the treatment effect in terms of hazard ratios and two-sided 95% CI. The cumulative steroid dose on Study Days 28, 56 and 90: descriptive statistics and non-parametric Wilcoxon-Mann-Whitney test stratified by for the baseline GvHD severity grade.
- Cumulative incidence of relapse up to Study Day 180 will be graphically displayed by non-parametric cumulative incidence curve estimates. The null hypothesis of same cumulative incidences (up to Study Day 180) for both study treatments will be tested by a one-sided test stratified for the baseline GvHD severity grade, taken into account the competing risk of death prior to diagnosis of relapse. Stratified regression analysis of cause-specific hazards will be performed as supportive analysis in order to quantify the treatment effect in terms of hazard ratios and two-sided 95% CI.
- Cumulative incidence of relapse-related mortality up to Study Day 180 will be graphically displayed by non-parametric cumulative incidence curve estimates. The null hypothesis of

same cumulative incidences (up to Study Day 180) for both study treatments will be tested by a one-sided test stratified for the baseline GvHD severity grade, taken into account the competing risk of transplant-related death (defined in Section 6.1.1.2). Stratified regression analysis of cause-specific hazards will be performed as supportive analysis in order to quantify the treatment effect in terms of hazard ratios and two-sided 95% CI.

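### Does the multiple-imputation statement in section 8.3.8 override the rule that a missing Day 28 assessment counts as non-response?

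*Combined protocol and SAP*

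**What the plan says.** Section 8.3.8 covers missing data in three sentences. It promises suitable techniques for those efficacy endpoints to which they are relevant, then says "Multiple imputation will be used as the primary method for accounting for missing data", and refers to the SAP for details. It lists no endpoints and does not mention section 6.1.1.1.

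Section 6.1.1.1 deals with missing data inside the endpoint definition. The first limb of non-response reads "Stable disease or PD or missing response assessment at Study Day 28 (including death up to Study Day 28) or", and the second covers subjects given third-line therapy before the Day 28 assessment. Death is also listed as an outcome category of its own: "Death (up to Study Day 28". Section 6.2.4.2 repeats the treatment-failure element: "Addition of other agents prior to Study Day 28 would constitute failure to respond (endpoint OR at Study Day 28".

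Section 8.3.4 links the analysis to that definition: "OR at Study Day 28 (see Section 6.1.1.1) is the single primary" endpoint for the FDA. Section 8.2 fixes the denominator: "The FAS comprises all subjects to whom study treatment has been randomized". On timing, section 8.0 says "The SAP will be finalized prior to randomization of the first 30% of the planned number of subjects".

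**The concern.** Read alone, section 8.3.8 is a general statement that imputation comes first, with no exception for OR. A literal reader could impute a Day 28 response for subjects whom section 6.1.1.1 calls non-responders.

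OR is the first test in the FDA sequence and the second in the EMA sequence (section 8.3.5.1). It also carries the interim threshold of one-sided p below 0.001 for a conditional-approval submission (section 8.6). Treatment is open-label at the sites, so missingness could differ between arms. The two rules would then give different estimates and, in some trials, different verdicts.

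**Working it through.** **Step 1: do two rules act on the same datum?**

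| Question | Where answered | Answer |
|---|---|---|
| Who is analysed? | 8.2 | All randomized subjects |
| Which definition does the OR test use? | 8.3.4 | The one in 6.1.1.1 |
| Day 28 assessment missing, subject alive | 6.1.1.1 | Non-response |
| Death by Day 28 | 6.1.1.1 | Non-response |
| Third-line therapy before the assessment | 6.1.1.1, 6.2.4.2 | Non-response |
| Otherwise | 6.1.1.1 | By adjudicated CR, PR, SD or PD |

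The categories are exhaustive, so OR has a value for every randomized subject and imputation has nothing to work on.

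The wider reading also proves too much. If section 8.3.8 overrode endpoint-specific rules, it would equally displace the censoring rules for TRM (6.1.1.2), OS (6.1.2.1), chronic GvHD (6.1.2.3) and relapse (6.1.2.5). The narrower reading leaves it a use. Section 8.3.5.2 has "The cumulative steroid dose on Study Days 28, 56 and 90: descriptive statistics and non-parametric Wilcoxon-Mann-Whitney test", and neither it nor section 6.1.2.4 says what to do with missing doses.

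**Step 2: the plan's own figure.** Inputs from section 8.1: 50% versus 75%, one-sided 0.025, 80% power. With pooled variance under the null and no continuity correction:

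n = [1.960 × √(2 × 0.625 × 0.375) + 0.842 × √(0.25 + 0.1875)]² / 0.25² = (1.342 + 0.557)² / 0.0625 = 57.7, so 58 per arm, as stated. At 184/2 = 92 per arm the power is 94.5%.

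**Step 3: what if the rules did compete?** The documents give no missing rates, so those below are assumptions, shown as BEGEDINA/control. Under the non-response rule the expected rate in an arm is p(1 − m) over 92 subjects. Imputation is approximated by available cases: the rate stays at p, with 92(1 − m) subjects.

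Example at 10%/3%: 0.75 × 0.90 = 67.5% and 0.50 × 0.97 = 48.5%, a difference of 19.0 points. The pooled rate is 58.0%, the standard error √(2 × 0.58 × 0.42/92) = 0.0728, z = 2.61 and one-sided p = 0.0045.

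| Missing | Non-response: difference, p | Imputation: difference, p |
|---|---|---|
| 5%/5% | 23.75 points, 0.0005 | 25.0 points, 0.0003 |
| 3%/10% | 27.75 points, 0.00007 | 25.0 points, 0.0003 |
| 10%/3% | 19.0 points, 0.0045 | 25.0 points, 0.0004 |

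The expected result is significant under both rules in all three cases.

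**Step 4: single trials.** Simulated with the stratified Cochran-Mantel-Haenszel test: 75% versus 50%, 200,000 trials, two strata of 46 per arm (equal strata assumed), same available-case approximation.

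| Missing | Power, non-response | Power, imputation | Verdicts differ |
|---|---|---|---|
| 2%/2% | 93.3% | 94.1% | 2.0% |
| 5%/5% | 91.0% | 93.4% | 3.9% |
| 10%/10% | 86.7% | 92.0% | 7.2% |
| 8%/5% | 84.0% | 92.9% | 9.2% |
| 3%/10% | 97.1% | 93.0% | 4.4% |
| 10%/3% | 73.7% | 92.8% | 19.1% |

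At a smaller assumed effect, 65% versus 50%, verdicts differ in 8.9% of trials at 5%/5%, 17.4% at 3%/10% and 24.9% at 10%/3%. Running 50 imputations per trial (unstratified, 20,000 trials), with deaths held as non-response, gave similar results at 75% versus 50%: 4.0% at 5%/5% and 19.5% at 10%/3% with no early deaths, and 4.6% and 19.8% with 10% early deaths per arm.

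**The case for a change.** The best case for a change has three parts.

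First, the narrow reading leaves section 8.3.8 little to do. The time-to-event endpoints have censoring rules, organ stage and Karnofsky status are shift tables, and the exploratory endpoints are descriptive. Cumulative steroid dose is the only formally tested endpoint without a rule. That is a fair remark on the drafting. But a general sentence that turns out to have a narrow scope does not cancel a specific definition.

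Second, neither rule is always conservative. With a true response of 50% in both arms, and 10% missing on control against none on BEGEDINA, the non-response rule compares 45% with 50% and rejects in about 10.0% of trials by the normal approximation. With the missingness reversed it rejects in about 0.4%. This stands, but it bears on which rule is better, and section 6.1.1.1 has made that choice. It does not show that the choice is unclear.

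Third, blinding and the early SAP date do not themselves rank the rules. That is true. They do limit the harm: 30% of 184 is about 55 subjects, so the SAP is due well before the interim analysis at about half of the subjects (about 92), and the study team is blinded with listed exceptions (section 5.6).

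The largest disagreement needs more missing assessments on BEGEDINA. Nothing in the documents points that way: that arm has an infusion at the center on Day 28, and subjects who stop treatment are asked to stay for endpoints (section 4.4.4.2).

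**Conclusion.** The concern does not call for a change. The missing cross-reference is real, but the OR definition, the pointer to it in section 8.3.4 and the all-randomized analysis set together settle the primary analysis: a missing Day 28 assessment is non-response, and so is death by Day 28. This is a detail that analysts will fill sensibly. A line in the SAP confirming it would be tidy, and an imputation-based sensitivity analysis of OR in survivors without an assessment is optional.

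If the rules were nevertheless confused, verdicts would differ in about 2% to 4% of trials with 2% to 5% missing in each arm at the planned effect. The figures of 19% to 25% arise only at 10% missing on BEGEDINA and 3% on control, the upper one at a smaller effect than planned. All of these figures rest on assumed missing rates and on a simple stand-in for an imputation model that the protocol does not specify. The SAP's own text on missing data was not available, so the conclusion rests on the protocol sections cited.
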